Unfortunately, hospital-acquired weakness is highly prevalent among COVID-19 patients, who require paralytics for an extended period of time in order to maintain oxygenation. The prolonged use of these agents lead to long-term inhibition of the Acetylcholine receptors of Neuromuscular junctions. All COVID-19 ventilated patients at our institution have been on paralytics for at least 48 hours, and most of these patients receive concomitant Glucocorticoid therapy. Together Glucocorticoids and paralytics, lead to Myosin depletion and muscle atrophy. This combination has shown to be a risk factor for CINM. In a recent JAMA study on 5700 COVID-19 patients performed in NYC, 72% of the ventilated patients remained in the hospital, and only 3% of this population have been discharged. We believe that the major reason for this is the inability to wean from the ventilator and to rehabilitate due to Neuro-Myopathy.

A recent systematic review suggested the major pathways involved in CINM. These major pathways include muscle disuse due to prolonged immobilization, inflammation, impaired perfusion and oxygen delivery, and hyperglycemia. All these factors might be magnified among COVID-19 patients. Additional to muscle atrophy, a hyper-inflammatory systemic state and coagulation disorders induced by the COVID-19 virus, poor blood oxygen saturation, and poor perfusion to lower extremities are other important risk factors to be aware in these patients. As described above, this type of work may allow physicians to provide more personalized care and evaluate their interventions with a practical test.

Muscle weakness and fatigue impede patients; capacity to exercise, and are known to delay extubation, extend length of stay in hospital, and delay patients to achieve independent mobility. The goal of E-stim in advanced disease states is to prevent or reverse skeletal muscle wasting for persons who are not able to exercise. Conditions include advanced periods of mechanical ventilation.

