Will pregnant women and/or fetuses (as described in 45 CFR 46 Subpart B) be enrolled in the research? No

E4. Neonates

Will neonates of uncertain viability or nonviable neonates (as described in 45 CFR 46 Subpart B) be enrolled in the research? No

E5. Children

Will children be enrolled in the research? No

Section F: Design/Procedure

F1. Design

Select one category that most adequately describes your research: c) Pilot

Discuss the research design including but not limited to such issues as: probability of group assignment, potential for subject to be randomized to placebo group, use of control subjects, etc.

Phase I: 20 subjects with COVID-19 infection that are being treated in the hospital. This means that this patient population is positive to COVID-19 and have been admitted with no more than 48 hours to the hospital due to severe infection. In some cases, the patients will not able to consent at the time of enrollment. This determines a high grade of severity of illness. Therefore, a family member/legal representative will be contacted via telephone for consenting. Participants will be randomized to intervention (IG) or control group (CG). The entire cohort will receive daily EE in lower extremity (e.g. Gastronemius, tibial anterior muscle) up to 1 hour. EE therapy will be provided using portable device. The EE device will be functional for IG and non-functional for CG. The duration of the study will be 2 weeks or until patient discharge, whichever comes first. The primary outcomes include between group difference and change from the baseline in muscle endurance, muscle strength, lower extremity tissue oxygen saturation, neuropathy, and muscle atrophy. Outcomes will be assessed at baseline, time of discharge or 2 weeks, whichever comes first. Due to the condition of the patient we are looking to reduce the interaction with staff, the device will be placed with no additional requirements. Physical therapy targets other physical performances, this device is aimed to improve blood flow, tissue perfusion and muscle activation while the patient is non-responsive to physical activities.

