Aim1 (to understand mechanism of action): Examine immediate benefit of lower extremity EE to improve venous return flow, tissue oxygenation, and muscle activation (short term benefit). In this study, we will recruit a convenient sample of 20 hospital patients diagnosed with COVID-19 (short-term benefit).

Optional: Subjects will be assessed using Doppler ultrasound and near infrared imaging (Kent Imaging System) at pre-, 30min, 60min, and 30min post-treatment (after stopping of EE device). Lower extremity muscle activation will be assessed by using sEMG (electromyography).

Patients will begin the study after being admitted to the hospital no more than 48 hours.

Aim 2 (to examine effectiveness): Examine effectiveness of daily use of EE to treat CINM, and other associated major adverse events (MAE) including deep vein thrombosis (DVT), cardiovascular events, and death. Participants will receive standard of care plus adjunctive daily EE therapy using an FDA approved bio-electric stimulation technology (BEST) platform (Tennant Biomodulator® PRO, AVAZZIA, Inc) during the entire length of stay in hospital. The device will be provided by the research staff.

We will assess incidence of neuropathy and myopathy during hospital discharge or 2 weeks, whichever comes first. Neuropathy severity will be quantified using vibratory perception threshold (VPT) test. Myopathy will be assessed by measuring changes in calf muscle circumstance, weight change from pre-hospital admission, and sEMG. In addition, we will determine weakness using foot dynamometer and a validated frailty meter. Length of hospital stay and MAE (documented via electronic health record) will be tracked for planning of future studies. Both extremities will have all measurements and 1 hour electrical stimulation therapy at baseline. Daily treatment will performed up to 3 times per day, but no more than 1 hour in total.

Daily electrical stimulation will be administered by a nurse/staff involved in the hospital care. A chart will be signed to register each therapy performed and will include a log of day and time of device application.

Both electrical stimulation and EMG devices will have disposable pads, after usage they will be discarded. For the Devices they will be placed inside a plastic bag that will be disposed inside the room before exiting and sanitized (wipes) based upon hospital protocols.

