activation. The device is used to reduce pain. However, the proposed treatment may assist in preventing or improving hospital-acquired Weakness because of prolonged hospital stay . In addition, the participation in this study may help the investigators better understand how COVID19 may impact cause myopathy and neuropathy and how to best help these patients to recover from prolonged hospital-stay .

Primary outcomes include neuropathy (assessed using VPT test); muscle function (assessed using sEMG), and tissue oxygenation (assessed using Kent Imaging). Secondary outcomes include weakness (assessed using dynamometer); muscle atrophy (assessed by weight loss as well as measuring ankle, calf, and thigh circumference); venous return flow (Doppler US [optional]); frailty (frailtymeter [optiona]); hospital length of stay (patient medical record); and major adverse events (patient health record). The primary and secondary outcomes will be assessed at baseline (if feasible) and on biweekly basis up to 4 weeks or hospital discharge, whichever came first. Appropriate mixed models (linear for continuous or Generalized Estimating Equations (GEEs) for non-continuous or non-parametric variables) will be used to test the intervention effect for each of the primary (e.g., tissue perfusion, tissue oxygen delivery, neuropathy severity, and myopathy incident) or secondary (e.g., frailty, weight loss, MAE, etc) outcomes.

Also, participation may help the investigators design a practical assessing method to identify the impact of neuromyopathy in the hospital setting. This may allow physicians to provide personalized care by monitoring muscle loss and limb complications caused by prolonged hospital length of stay.

Describe potential benefit(s) to society of the planned work.

As described above, this type of work may allow physicians to provide more personalized care for hospitalized patients in need of physical therapy for continuous and prolonged periods, specially when having a severe illness that includes medical staff risk contact.

Do anticipated benefits outweigh potential risks? Discuss the risk-to-benefit ratio.

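### Length of stay and major adverse events have conflicting follow-up limits in Phase I, and the plan has no rule for an in-hospital death in the length-of-stay analysis

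*Combined protocol and SAP*

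**What the plan says.** Three parts of the document bear on how long these two outcomes are followed in Phase I.

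- **Section I (outcomes paragraph)** lists among the secondary outcomes "hospital length of stay (patient medical record); and major adverse events (patient health record"). The next sentence applies one schedule to every primary and secondary outcome: assessment at baseline if feasible, then "on biweekly basis up to 4 weeks or hospital discharge, whichever came first". It makes no exception for length of stay or MAE.
- **Section F1, Phase I** gives a shorter limit: "The duration of the study will be 2 weeks or until patient discharge, whichever comes first". It adds: "Outcomes will be assessed at baseline, time of discharge or 2 weeks, whichever comes first".
- **Section F2, Phase I, Aim 2** names no limit: "Length of hospital stay and MAE (documented via electronic health record) will be tracked for planning of future studies". The same aim describes therapy as given "during the entire length of stay in hospital", and counts deep vein thrombosis (DVT), cardiovascular events and death as MAE.

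On analysis, Section I offers linear mixed models for continuous outcomes and GEE for others, to test the intervention effect on each primary or secondary outcome. Section G2 adds only that each variable uses all available data. Nowhere does the document define when a stay starts and ends, or say how a patient who dies in hospital, or is still there when assessments stop, enters the length-of-stay analysis.

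**The concern.** The background in Section C gives reason to expect long stays. In the series it cites, "72% of the ventilated patients remained in the hospital, and only 3% of this population have been discharged". Phase I enrols within 48 hours of admission, so a patient with a long stay could still be in hospital at 2 weeks, or at 4.

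If follow-up stops with the functional assessments, three things go wrong. Stays beyond the limit are recorded at the limit, which shrinks any true difference between arms and understates the standard deviation. MAE after the limit are not counted, although Aim 2 is partly about MAE. And if a death simply ends the stay, an arm with more early deaths shows a shorter mean stay and looks better for it.

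Section F2 says these data are for planning later studies. A shrunken difference and a standard deviation that is too small would go straight into the next sample size calculation.

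**Working it through.** **Figures in the plan.** There is no length-of-stay figure to reproduce. The sample size is one of convenience; the only sum to check is 20 (Phase I) + 20 (Phase II) = 40, which agrees with Section G1.

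**The follow-up limits side by side.**

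| Place | Applies to | Limit |
|---|---|---|
| F1, Phase I | the study, and its outcomes | 2 weeks or discharge |
| I, outcomes paragraph | all primary and secondary outcomes | 4 weeks or discharge |
| F2, Phase I, Aim 2 | length of stay and MAE, from the health record | none stated |

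These cannot all govern length of stay. The first two give different limits, and the third gives none.

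**Effect of a limit on the mean difference (assumed stays).** Take stays as gamma with shape 2 and scale θ. Then:

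- the median is 1.678θ and the mean is 2θ
- the proportion staying beyond day c is (1 + c/θ)e^(−c/θ)
- the mean of the stay limited at c is 2θ − (2θ + c)e^(−c/θ)

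For medians of 21 v 14 days, θ = 21/1.678 = 12.51 and 14/1.678 = 8.34. The unlimited means are 25.0 and 16.7, a difference of 8.3 days. With a 14-day limit the means are 12.28 and 10.96, a difference of 1.3. With a 28-day limit they are 19.37 and 15.13, a difference of 4.2. The same steps for two other pairs give:

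| Assumed medians | No limit | 28-day limit | 14-day limit | Longer-stay arm beyond day 28 / day 14 |
|---|---|---|---|---|
| 28 v 20 days | 9.5 | 3.0 | 0.75 | 50% / 79% |
| 21 v 14 days | 8.3 | 4.2 | 1.3 | 35% / 69% |
| 7 v 5 days | 2.38 | 2.34 | 1.79 | 1% / 15% |

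The 21-day arm has a standard deviation of 17.7 days (θ√2) without a limit, 8.5 with a 28-day limit and 3.2 with a 14-day limit.

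**Second distribution.** With log-normal stays (log-SD 0.7) and a true 25% shorter stay, the mean difference is 4.5 days without a limit, 3.1 at 28 days and 1.4 at 14 days for a median of 14. For a median of 21 it is 6.7, 3.1 and 0.95. The shrinkage is 31% to 54% at day 28 and 69% to 86% at day 14.

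**Effect of a death recorded as the end of a stay.** With 10 patients per arm (1:1 is assumed; the Phase I ratio is not stated), one death on day 4 in place of a 20-day stay lowers the arm mean by (20 − 4)/10 = 1.6 days. More generally, each extra 10 percentage points of deaths lowers the mean by 0.10 × (mean stay − mean day of death). In the log-normal model this is 0.10 × (17.9 − 7) = 1.1 days for a median of 14 and death on day 7. It is 0.10 × (26.8 − 5) = 2.2 days for a median of 21 and death on day 5. Survivors' stays are unchanged in both cases.

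**The stated analysis.** A patient has one length of stay, so a linear mixed model has no repeated measures to use and in effect compares means. Neither it nor a GEE, as described, separates a stay that ended in discharge from one that ended in death or had not ended.

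**The case against.** The strongest reply is that the plan nowhere says stays are capped. Length of stay comes from the medical record, and Section F2, the only place that describes its collection, sets no end date. The biweekly schedule in Section I fits repeated bedside measures; a length of stay cannot be assessed at baseline or every two weeks. The primary-outcome list that follows the 2-week sentence in Section F1 does not include length of stay. This stands. A reader might infer from Sections F1 and I that stays are cut at 2 or 4 weeks, but that is one literal reading, and Section F2 prevents it from being a certainty.

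Likewise, a reader might infer that the plan counts early deaths as short stays. It states no such rule. The risk comes from silence combined with a model for means, and deaths would in any case be collected as MAE.

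It is also fair that the stakes are limited. Phase I is a 20-patient pilot in which length of stay mainly serves planning. In the gamma model with 10 per arm, the standard error of the 21 v 14 comparison is √((17.7² + 11.8²)/10) = 6.7 days against a difference of 8.3, so no firm conclusion on stay is available with or without a limit. The series in Section C concerns ventilated patients, its follow-up time is not given, and ventilation is not an entry criterion here. If stays are short, a 28-day limit costs almost nothing.

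What remains is that the limits conflict, Section I makes no exception for length of stay or MAE, and no place says how death is handled. Low power does not answer this, because a truncated standard deviation would still be carried into the next trial.

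**Conclusion.** The concern holds as a conflict and an omission. The follow-up of length of stay and MAE is 2 weeks, 4 weeks or open-ended depending on the section read, and the named analysis cannot deal with an in-hospital death.

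The effect of applying a limit ranges widely with the assumed stays. A 14-day limit removes about 25% of a true difference at medians of 7 v 5 days (1 − 1.79/2.38) and about 84% at 21 v 14 (1 − 1.32/8.34). A 28-day limit removes about 2% (1 − 2.34/2.38) and 49% (1 − 4.24/8.34). All stay distributions and days of death used here are assumptions; the documents supply none. The impact on this pilot is modest, and the main consequence is for the planning use stated in Section F2. The point is worth correcting because the correction is cheap and the choice would otherwise be made after data are seen.

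**What to change.** 1. Reconcile the windows in Sections F1, F2 and I, so that one statement governs Phase I functional assessments and a separate one governs outcomes taken from the record.
2. State that length of stay and MAE are taken from the health record from randomisation to actual discharge or death, regardless of when functional assessments end.
3. Replace the linear model for length of stay with a descriptive summary of time to discharge alive: cumulative incidence by arm, with death as a competing event so that a death is never counted as a discharge.
4. Report deaths by arm beside that summary.

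This is a change of wording. The data source is already named, and no visit or procedure is added. The one small cost is that chart follow-up of the longest-stay patients finishes later.

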The researchers will take digital photographs /videos throughout the study. This is done using a special camera for tissue oxygen detection and visual images. This method is non invasive and does not cause any harm to the patient. **We will blur the face out in the photographs/videos. We will only use videos and photos for scientific presentations or scientific publications.

Phase II:

Patients will begin the study after incidence of muscle loss, muscle weakness, muscle pain, or neuromyopathy due to prolonged immobilization for COVID-19. This assessment will be performed by a critical care and pulmonary specialist at the BCM COVID-19 Clinic.

The protocol will consist of 4 weeks of lower-extremity electrical stimulation. This modality will consist of home-based therapy, meaning that the patient will take the device home and attend the clinic once a week for screening and assessment of therapy.

The protocol will be performed as the following description: This trial will have 20 patients divided in two groups. Group 1 (intervention, n=10): Will receive an active Tennant Biomodulator. Patients assigned the active device (active group; Group 1) at their initial visit (baseline) will only have 4 weeks of study participation (which includes 5 visits: Baseline (week 0), Visit 1 (Week 1 of at-home therapy), Visit 2 (Week 2 of at-home therapy), Visit 3 (Week 3 of at-home therapy), Visit 4 (Week 4 of at-home therapy). After 4 weeks, the patients will turn back the electrical stimulation device to the research staff.

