P-values of 0.05 or less will be considered statistically significant based on a two-sided test unless otherwise noted. All variables will be tabulated descriptively at each scheduled time point (baseline and discharge date). For each continuous variable, the analyses will include the mean, standard deviation, minimum and maximum. For each categorical variable, the summary will include frequencies and percentages. Each variable will be analyzed using all available data. Baseline variables will be summarized using descriptive statistics. We assume that a successful intervention is also helpful to maintain subjects muscle mass, reduce neuromyopathy signs and increase venous return flow. The measured parameters (e.g. muscle circumference, sEMG, kent imaging, doppler, etc.) should change substantially from baseline to the end of the intervention. For example, the EMG amplitude values should show increased voltages. Next, for all continuous variables, pre-treatment scores will be regressed on post-treatment scores to form residualized change scores (e.g. sEMG, VPT, dynamometer, etc). Correlations will then be generated among these scores to determine whether changes in sEMG factors are related appropriately with increases in (clinically assessed) functional capacities and self-report measures of activities. ANOVA test will be used to examine significant difference between patients with severe risk factors for prolonged ICU stage (e.g. age, BMI, cardiovascular morbidities). Moderator effects will also be examined for exploratory purposes. Using gender as an example, mixed design ANOVAs will be conducted to determine whether mobility factors change over the course of treatment at different rates or with different patterns for men and women. Additional analyses will test whether changes in muscle strenght and neuropathy (e.g. VPT and dynamometer assessement at time of discharge).

Section H: Potential Risks/Discomforts

H1. Potential Risks/Discomforts

Describe and assess any potential risks/discomforts; (physical, psychological, social, legal, or other) and assess the likelihood and seriousness of such risks:

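### GEE is planned for 20-patient phases with no variance estimator or small-sample method named, so its tests need not hold the stated 5% level

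*Combined protocol and SAP*

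**What the plan says.** The models are named in Section I (Potential Benefits), in the paragraph that lists the outcomes. Linear mixed models serve continuous outcomes, and "Generalized Estimating Equations (GEEs) for non-continuous or non-parametric variables" serve the rest. These models "will be used to test the intervention effect for each of the primary" and secondary outcomes. The primary examples there include "neuropathy severity, and myopathy incident", and the secondary examples include major adverse events.

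Section G2 sets the threshold: "P-values of 0.05 or less will be considered statistically significant based on a two-sided test".

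On numbers, F1 has "Phase I: 20 subjects with COVID-19 infection that are being treated in the hospital", randomised to two groups with no ratio given. For Phase II, F2 states: "This trial will have 20 patients divided in two groups", with 10 in each. G1 describes a sample of convenience.

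Nothing in the document names the variance estimator, working correlation, link, reference distribution or a small-sample correction for the GEE analyses.

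**The concern.** The empirical (sandwich) variance that normally accompanies GEE is justified for many independent clusters. Here the clusters are patients, about 20 per phase. At that number the uncorrected estimator is biased downward, and comparing the Wald statistic with a normal distribution adds to the error. Sparse binary data bring a different failure: the Wald test loses almost all its power or the model cannot be fitted.

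Either way, a p-value from an unspecified GEE would not carry the 5% meaning given in G2. The study is meant to show proof of concept and to inform later work. A spurious signal could steer that work, and so could a real effect missed because the test could hardly reject.

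**Working it through.** **Inputs from the documents.** Two-sided 0.05 (G2). 20 patients per phase; 10 per arm in Phase II (F2). Measurement occasions: two in Phase I (F1), five in Phase II (F2), and about three under the biweekly schedule in Section I.

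**Assumptions, because the documents give no figure.** 10 per arm in Phase I; within-patient correlation 0.5; binary prevalence 0.1 to 0.5; 8 or 6 evaluable per arm as sensitivity cases; uncorrected sandwich with a normal reference as the default. There is no power calculation to reproduce. The only stated figure to test is the 5% level.

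**Exact check, one normal value per patient.** With n per arm, GEE reduces to a difference in means with variance Σ s²_ML/n, where s²_ML = s²(n−1)/n. The test therefore rejects when an ordinary t statistic on 2n−2 degrees of freedom exceeds 1.96·√((n−1)/n).
- n = 10: 1.96·√0.9 = 1.859 on 18 df gives **7.9%**.
- n = 8: 1.833 on 14 df gives 8.8%.
- n = 6: 1.789 on 10 df gives 10.4%.

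The remedies in the same case, at n = 10:
- t(18) reference alone: 2.101·√0.9 = 1.993 gives 6.2%.
- Mancl-DeRouen with a normal reference: 1.96·√(10/9) = 2.066 gives 5.4%.
- Kauermann-Carroll cancels the (n−1)/n factor, so with t(18) it is the ordinary t-test: 5.0%. With a normal reference it gives 6.6%.

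**Simulation, repeated outcomes.** No treatment effect, 2,000 trials per scenario (Monte Carlo standard error about 0.5 points at 5%), exchangeable working correlation.

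| Outcome, 10 per arm | Uncorrected, normal ref. | Mancl-DeRouen, normal ref. |
|---|---|---|
| Binary, prevalence 0.3–0.5, 3 or 5 visits | 7.2–8.8% | 4.3–5.9% |
| Normal, all visit counts | 7.6–8.7% | 4.7–6.1% |
| Lognormal, 5 visits, arm-by-time | 7.2% | 4.8% |

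Across all lognormal runs the uncorrected rate was 5.8–7.2%. A separate set of 1,000-trial runs with binary prevalence 0.4 gave 6.6% at three visits and 5.8% at two; the latter cannot be told apart from 5%. In the 2,000-trial set, the two-visit arm-by-time test gave 7.0% at prevalence 0.5 but 4.8% at 0.3, so inflation is not uniform.

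With fewer evaluable patients (five visits, arm-by-time, binary prevalence 0.3–0.5), the uncorrected rate is 8.6–10.1% at 8 per arm and 10.0–14.7% at 6. Lognormal outcomes there give 7.4% and 8.5%.

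**Exact check, binary outcome measured once.** The logit Wald test was enumerated over all pairs of binomial counts at 10 per arm. It rejects in 3.9% of null trials at prevalence 0.5, 1.7% at 0.3, 0.4% at 0.2 and about 0% at 0.1. The chance that an arm has no events or all events, at prevalence 0.1, is 1 − (1 − 0.9¹⁰ − 0.1¹⁰)² = 1 − 0.6513² = **58%**. Mancl-DeRouen lowers the rejection rate further, to 1.0% at 0.5 and 0.3% at 0.3.

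**Rare binary outcome, five visits, prevalence 0.1, arm-by-time.** About 21% of usable fits reject, and 16–18% still do after Mancl-DeRouen. The variance correction does not rescue sparse data.

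**The case against.** The strongest reply is that the plan never mentions a robust or sandwich variance. That is right. A reader might infer that the plan chose one, but the documented gap is silence, and the figures above are conditional on a common default. Silence still matters at 20 patients, because nothing steers the analyst away from that default.

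A reader might also infer that every p-value at 0.05 is too liberal. The documents do not support this. The listed primary measurements (vibration threshold, surface EMG, tissue oxygenation) are instrument readings and go to linear mixed models unless judged non-parametric, a term the plan does not define. The outcomes that clearly belong to GEE are myopathy incidence and major adverse events.

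Nor does GEE always reject too often here. F2 assesses myopathy incidence at discharge or two weeks, which reads as one value per patient, and for that the Wald test is conservative. A blanket small-sample correction would make it more so. This stands, and it is why one remedy does not fit all outcomes.

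Finally, F1 classifies the study as a pilot and no decision rule hangs on a GEE p-value. That limits the consequence. It does not remove it, since the plan tests for significance on each outcome. No joint error rate across outcomes was computed, so none is claimed.

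**Conclusion.** The concern holds in a limited form: the GEE analyses are under-specified for 20 patients per phase, and the likely default does not deliver the stated 5%. For repeated binary outcomes of moderate prevalence, and for continuous outcomes routed to GEE, the true level is about 6–9%. It rises to about 8–10% or more, for five-visit binary outcomes and once-measured normal values, if only 6–8 per arm are evaluable. For a once-measured binary outcome it is 0–4%, often with no usable estimate when events are rare. Outcomes analysed by linear mixed models are outside this point.

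The sizes rest on the assumed default estimator, prevalence, correlation and evaluable numbers, and on 10 per arm in Phase I. The missing specification rests on none of these.

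**What to change.** In the analysis sentence of Section I, add text such as: *GEE analyses of repeated outcomes use a small-sample corrected sandwich variance (Mancl-DeRouen with a normal reference, or Kauermann-Carroll with a t reference). Binary outcomes measured once, or with few events, including myopathy incidence and major adverse events, are compared by an exact test or by penalised (Firth) logistic regression instead of GEE.* Choose one option in each pair before the data are seen, and list which outcomes go to GEE.

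For the exact test, an unconditional one is preferable. Enumerating the same tables at 10 per arm, Boschloo's test rejects in 4.2%, 3.7% and 0.9% of null trials at prevalence 0.5, 0.3 and 0.1, against 1.3%, 1.2% and 0.1% for Fisher's. Both are always computable.

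The cost is slightly wider intervals and a little more analysis work. Two limits remain. At 6 evaluable per arm, five visits and prevalence 0.3, Mancl-DeRouen with a normal reference still gives 8.9%. Kauermann-Carroll was checked here only in the single-value normal case, and Firth regression was not checked.

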Group 2 (control, n=10): Will receive an inactive Tennant Biomodulator for 4 weeks. The control group will have the option to receive an active device after their 4 weeks visit. Should they agree, they would receive at-home therapy for another 4 weeks and come to the clinic for up to two additional visits for assessment. If the subject agrees to receive the active device at the 4th week visit (visit 4), then they will only be required to attend the clinic for one more visit (visit 5). For subjects in this group that were previously enrolled (i.e. Visit 4 completed), they will be contacted to be unblinded and confirm agreement/reconsent to have another 4weeks of study participation with an active device. They will have 2 additional visits (visit 5 and Visit 6). Visit 5 will consist of the same procedures and one hour of stimulation than visit 4, and the subject will receive an active device to take for additional 4 weeks and come back to the clinic for a final assessment (Visit 6). Visit 6 will consist of the same procedures and one hour of stimulation the subject will return the active device at their last visit (either Visit 5 or Visit 6 depending on the conditions listed above).

Group 2 will consist up to 7 visits total with possible phone calls in between. The patient will be compensated \$50 per inperson, clinic visit (total \$350), with free parking. Payment will only be available for subjects who participate in Part II.

During Visit 1, Visit 2, Visit 3, the the research staff will turn the Tennant Biomodulator PRO® on for 5 minutes and measure any changes in muscle strength, endurance, and blood flow after the therapy.

During Baseline, Visit 4, Visit 5, Visit 6, the research staff will turn the Tennant Biomodulator PRO® on for one hour and measure any changes in muscle strength, endurance, and blood flow after the therapy. Once the Baseline is over, the patient will take the Tennat Biomodulator® home and will be instructed to turn it on for one hour every day for four weeks.

Any study visits may include the following assessments in addition to electrical stimulation: 1) Questionnaires (pain, weakness, sleep, quality of life, frailty, depression, life and space, beck anxiety scale, Katz-daily living, fatigue) 2) Musculoskeletal assessments (non-invasive surface electromyography, vibration perception threshold, leg circumference measurement, ankle strength test) 3) Vascular assessments (non-invasive Near infra-red spectroscopy)

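### Section I tests major adverse events by GEE with about 10 patients per arm, but gives no link, small-sample correction or rule for an arm with no events

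*Combined protocol and SAP*

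**What the plan says.** Section I (Potential Benefits) lists MAE as a secondary outcome. It assigns linear mixed models to continuous variables and GEE to non-continuous ones, to test the intervention effect on each of the primary "or secondary (e.g., frailty, weight loss, MAE, etc) outcomes". It names no link, working correlation, test type or small-sample correction, and no fallback for sparse or absent events.

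Section F2 (Phase I, Aim 2) defines MAE as including "deep vein thrombosis (DVT), cardiovascular events, and death" and places them under an aim headed as effectiveness. The same aim then says that length of stay and MAE "will be tracked for planning of future studies".

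Section G2 sets the decision rule: "P-values of 0.05 or less will be considered statistically significant based on a two-sided test unless otherwise noted". It mentions neither GEE nor MAE by name.

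On size, Section F1 gives "Phase I: 20 subjects with COVID-19 infection that are being treated in the hospital" and randomizes them to two groups without a ratio. Section F2 gives the Phase II arms: "Group 1 (intervention, n=10): Will receive an active Tennant Biomodulator" and "Group 2 (control, n=10): Will receive an inactive Tennant Biomodulator for 4 weeks".

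**The concern.** A binary outcome with about 10 patients per arm can easily leave one arm without an event. Under a logit link the estimated log odds ratio then runs off to infinity. A robust standard error gives no protection, because it can stay small while the estimate diverges. The printed Wald p-value can therefore be extremely small when the data hold almost no information.

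The outcome includes death, so a spurious significant result in either direction would be misleading. If the analyst does notice the problem, the replacement analysis has to be chosen after the events are known. The two sections also disagree on whether MAE are tested at all.

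**Working it through.** The plan states no MAE rate, power or event-based sample size, so there is no figure of its own to reproduce.

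**Inputs.** Two-sided 0.05 (Section G2). Arms of 10 (stated in F2 for Phase II; for Phase I, 20 in total with 1:1 allocation assumed). Event rate p is an assumption, shown over a range.

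**Step 1: chance of an empty arm.** With n = 10 and the same rate in both arms, let q = (1 − p)^10 be the chance that one arm has no events.

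- Exactly one arm empty: 2q(1 − q)
- Both arms empty: q²
- At least one arm empty: 1 − (1 − q)²

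For p = 0.10: q = 0.349; exactly one = 2 × 0.349 × 0.651 = 0.454; both = 0.122; at least one = 0.576.

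| Assumed rate | q | Exactly one empty | Both empty | At least one empty |
|---|---|---|---|---|
| 5% | 0.599 | 48% | 36% | 84% |
| 10% | 0.349 | 45% | 12% | 58% |
| 20% | 0.107 | 19% | 1% | 20% |
| 30% | 0.028 | 5% | 0.1% | 6% |
| 40% | 0.006 | 1% | <0.1% | 1% |

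The exactly-one column matters most here. When both arms are empty, no method can show an effect. At least one empty arm is more likely than not only below a rate of about 12%.

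**Step 2: sensitivity.**
- An 8:12 split in Phase I gives at least one empty arm in 59% at a 10% rate and 22.5% at 20%, close to the equal split.
- If treatment halved the rate, exactly one arm would be empty in 38% (20% v 10%), 21% (30% v 15%) and 11% (40% v 20%).
- If the phases were pooled at 20 per arm, at least one arm would be empty in 59%, 23% and 2% at rates of 5, 10 and 20%.

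**Step 3: what a logit GEE returns.** Fitted with a standard GEE routine (Python statsmodels, robust standard errors), 10 per arm:

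| Events | Log OR | Robust SE | GEE p | Fisher p |
|---|---|---|---|---|
| 1/10 v 0/10 | −21.4 | 1.10 | 5.5e-84 | 1.0 |
| 3/10 v 0/10 | −22.7 | 0.76 | 8.1e-197 | 0.21 |
| 5/10 v 0/10 | −23.6 | 0.71 | 1.6e-243 | 0.033 |

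The log odds ratios only mark where the iteration stopped; no finite solution exists. Repeated records do not help: a data set with two visits per patient and one empty arm was reported as converged, with p about 5e-242.

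**Step 4: alternatives.** An identity-link GEE (risk difference) stays finite with one empty arm: 3/10 v 0/10 gives −0.30, SE 0.145, p = 0.038. Its uncorrected Wald test has a true size of about 9% at common rates of 20 to 40%, so it too would need a stated correction. Fisher's exact test has a true size of 0.1, 0.8, 1.2 and 1.3% at common rates of 10, 20, 30 and 40%.

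**The case against.** Four points weigh against reading too much into this.

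- **Frequency.** A reader might infer that the analysis will usually break down. The documents do not support that, because they give no MAE rate. Phase I enrols critically ill inpatients and the composite includes death, so a rate of 30% or more is possible, and an empty arm is then uncommon (6% or less). This stands. Against it, no single component can be more frequent than the composite, and Phase II patients are alert and treated at home, so lower rates are also possible.
- **Scope.** A reader might infer that GEE as such fails. Section I names GEE without a link, and an identity link gives a finite estimate when one arm is empty. This stands too, but that route is not specified and its uncorrected test is anti-conservative. A reader might also infer that GEE is pointless because MAE is one record per patient. The text does not say so: Section I has outcomes assessed every two weeks.
- **Harm.** A reader might infer that the planning data would be lost. Section G2 already tabulates every categorical variable by number and percent, so the counts survive a failed model, although G2 does not say the table is by arm.
- **Weight.** MAE is one secondary outcome in a self-described pilot with a convenience sample, and no decision in the plan depends on its p-value. This limits the importance of the point but does not remove it.

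**Conclusion.** The concern holds in a bounded form. Section I commits to testing MAE by GEE at about 10 per arm without a link, a small-sample correction or a zero-event rule, and this conflicts with the tracking-only role in Section F2. If the usual logit link is used, exactly one empty arm (48, 45, 19, 5 and 1% at assumed common rates of 5, 10, 20, 30 and 40%) leaves no finite treatment effect. Software can then report a spurious p-value that meets the 0.05 rule.

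This rests on three assumptions: the event rate, 1:1 allocation in Phase I, and a logit link. The silent failure was seen in one package; others may warn. It is worth correcting before analysis, but it does not threaten the trial's main purpose.

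**What to change.** In Section I, take MAE and its components out of the GEE rule. State instead that, for MAE and for each component, the number of patients with an event will be reported per arm, with the risk difference and an exact 95% confidence interval, as a descriptive summary. This brings Section I into line with the tracking role in Section F2 and adds the by-arm layout that G2 leaves open. If a p-value is wanted, name an exact test in advance and label it descriptive.

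The change costs one line of text. The statistical price is real: exact methods are markedly conservative at this size. Fisher's true size is about 0.1 to 1.3% against a nominal 5%, and with one empty arm it needs 5 events against 0 to reach significance (p = 0.033; 4 against 0 gives 0.087). That is acceptable for a descriptive secondary outcome in a pilot.
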